8.7.2 Reporting of SAEs to Health Authorities and REC/REB

The study CRO will be responsible for reporting expedited and non-expedited SAEs that are deemed possibly related to study vaccine and unexpected (unexpected refers to events that do not appear in the package labeling or in the study vaccine IB) to regulatory authorities.

The investigator will be responsible for reporting all SAEs directly to the relevant ethical review body (REC/REB) as soon as possible, and will also provide the ethical review body with any safety reports prepared by the PV group at the study CRO.

All SAEs that are considered SUSAR should be reported to Regulatory Authorities by phone or by facsimile transmission as soon as possible but in no event later than seven calendar days for deaths and life- threatening adverse events and 15 calendar days for other SAEs after the Sponsor's initial receipt of the information; and should be followed to resolution, stabilization, or return to baseline regardless of conclusion of the study.

8.8 Follow-up of AEs and SAEs

Follow-up during the study

After the initial SAE report, the investigator is required to proactively follow each participant and provide additional relevant information by completing an SAE Reporting Form (Follow-up report) on the participant's condition to the PV group at the study CRO.

All SAEs documented at a previous visit/contact and designated as not recovered/not resolved or recovering/resolving will be reviewed at subsequent visits/contacts until the end of the study.

All AEs documented at a previous visit/contact and designated as not recovered/not resolved or recovering/resolving will be reviewed at subsequent visits/contacts until Day 336 (EOS).

With the exception of medically attended adverse events (MAAEs), all AEs documented at a previous visit/contact and designated as not recovered/not resolved or recovering/resolving will be reviewed at subsequent visits/contacts until Day 336 (EOS).

Follow-up after the participant is discharged from the study

The investigator will follow participants:

- with SAEs or participants withdrawn from the study as a result of an AE, until the event has resolved, subsided, stabilized, disappeared, or until the event is otherwise explained, or the participant is lost to follow-up.
- with MAAEs until the end of the study or the participants are lost to follow-up.
- with other non-serious AEs, until Day 336 (EOS) or they are lost to follow-up.

If the investigator receives additional relevant information on a previously reported SAE, he/she will provide this information to the PV Group at the study CRO (via 24/7 Safety Line) by completing a paper SAE Pregnancy Reporting Form, as applicable.

The PV Group or Medical Director at the study CRO may request that the investigator performs or arranges the conduct of additional clinical examinations/tests and/or evaluations to elucidate as fully as possible the nature and/or causality of the AE or SAE. The investigator is obliged to assist. In the event of a participant's death during participation in the study or during a recognized follow-up period, the PV Group at the study CRO will be provided with any available post-mortem findings, including histopathology.

8.9 Treatment of Adverse Events

Treatment of any AE is at the sole discretion of the investigator and according to current good medical practice. Any medication administered for the treatment of an AE should be recorded in the participant's *eCRF*.

Participant card

Study participants must be provided with the address and telephone number of the main contact for information about the clinical study.

The investigator (or qualified designee) must therefore provide a "participant card" to each participant. In an emergency situation this card serves to inform the responsible attending physician that the participant is in a clinical study and that relevant information may be obtained by contacting the investigator.

The participant card will indicate the following:

- Study name
- Study number
- Participant number
- Investigator's name and 24-hour contact telephone number
- Back-up phone number in case investigator is unavailable
- Enrollment date
- Expected study duration
- Any other information that is required to do an emergency breaking of the blind

Participants must be instructed to keep participant cards in their possession at all times.

9 PARTICIPANT COMPLETION AND WITHDRAWAL

9.1 Study Completion

A participant who returns for the End-of-Study Visit is considered to have completed the study.

9.2 Study Vaccine Discontinuation

In rare instances, it may be necessary for a participant to permanently discontinue study vaccination. Reasons for vaccine discontinuation may include the following:

- Non-serious AE / SAE
- Positive SARS-CoV-2 (PCR or rapid antigen test)
- Participant request
- Investigator request
- Pregnancy
- Protocol deviation (including no longer meeting all the inclusion criteria, or meeting 1 or more exclusion criteria)
- Other (specify)

Note that discontinuation of study intervention does not represent withdrawal from the study. If study vaccination is permanently discontinued, the participant will remain in the study to be evaluated for safety, immunogenicity, and efficacy.

9.3 Study Discontinuation

A participant may withdraw from the study at any time at his/her own request. Reasons for discontinuation from the study may include the following:

- Refused further follow-up
- Lost to follow-up
- Death
- Study terminated by sponsor
- Non-serious AE / SAE
- Participant request
- Investigator request
- Protocol deviation.
- Other (specify)

If a participant does not return for a scheduled visit, every effort should be made to contact the participant. All attempts to contact the participant and information received during contact attempts must be documented in the participant's source document. In any circumstance, every effort should be made to document participant outcome, if possible.

Participants who are withdrawn because of SAEs/AEs must be clearly distinguished from participants who are withdrawn for other reasons. Investigators will follow participants who are withdrawn as result of a SAE/AE until resolution of the event.

Withdrawals will not be replaced.

10 STATISTICAL METHODS

10.1 Outcome Measures

10.1.1 Primary Endpoints/Outcome Measures

Rate and severity of local and systemic solicited adverse events (AEs) during 7 days after each study vaccination

Rate and severity of unsolicited AEs at Study during 28 days after each study vaccinations

Rate and severity of medically attended adverse events (MAAEs) during 28 days after each study vaccinations

Rate of serious adverse events (SAEs) during 28 days after each study vaccinations AEs leading to discontinuation of study vaccination

AEs leading to study discontinuation

Rate and severity of laboratory abnormalities (hematology, biochemistry, urinalysis) at Day 56 and 28 days after each study vaccination

10.1.2 Secondary Endpoints/Outcome Measures

Rate and severity of unsolicited AEs throughout the study

Rate and severity of medically-attended adverse events (MAAEs) throughout the study Rate of serious adverse events (SAEs) throughout the study

Rate and severity of laboratory abnormalities (hematology, biochemistry, urinalysis) throughout the study

- GMT and the geometric mean fold increase in serum antibody titer post-vaccination over Day 1 (baseline) at Days 56 and 224 (Phase 1a) or Days 56 and 168 (Phase 1b):
 - Neutralizing activity against multiple variant spike protein-expressing pseudovirus, and/or PRNT neutralizing activity against wild-type SARS-CoV-2 virus and the variant Beta (B.1.351) in all participants
 - RBD antibody titers against wild-type variant spike protein measured by ELISA
- GMT and the geometric mean fold increase in serum antibody titer post-vaccination over Day 1 (baseline) at Days 7, 28, 35, 56, 112, 224 and 336 (Phase 1a); Days 7, 14, 28, 56, 84, 168 and 336 (Phase 1b)
 - Neutralizing activity against multiple variant spike protein-expressing pseudoviruses, and/or PRNT neutralizing activity against multiple variants of SARS-CoV-2 virus and the variant (B.1.351) in all participants
 - RBD antibody titers against wild-type variant spike protein measured by ELISA

10.2 Determination of Sample Size

A total of approximately 60 participants will be enrolled in Phase 1a and approximately 54 participants in Phase 1b. The participants in Phase 1a will be randomized at 2:1 to VBI-2902a or placebo. Participants in Phase 1b will be randomized 1:1 to receive one dose of VBI-2905a or placebo.

With ~10% drop-out rate it is estimated that at least 56 participants will complete Phase 1a and 48 participants will complete Phase 1b. The sample size per active group will allow for the detection of at least a two-fold difference in nAb titers with 80% power and an alpha error of 0.05.

10.3 Immune Responses

Neutralizing antibody titers and binding antibody titers directed against the spike protein and its RBD region as well as cell-mediated immunity will be measured. This study is a first-in-humans study. Any immunogenicity results are intended to be exploratory and as such, no formal power calculation is reported.

10.4 Randomization

Treatment allocation for Phase 1a and Phase 1b will be done through an interactive response technology (IRT) system (interactive web response system, IWRS). Access to the IWRS will be through individual login and password. To enroll a new subject, the authorized staff at the site will be prompted to complete a randomization page including the subject's age, and other demographic information and to confirm individually the presence of all inclusion criteria, and the absence of all exclusion criteria. Upon confirmation that all inclusion criteria and no exclusion criteria are met the subject will be randomized. Blinded confirmation of the randomization will be sent by E-mail to the site and should be retained in the study files. The site pharmacy and/or unblinded study center staff will receive a notification for a unique subject randomization assignment, which must be filed in a locked area/computer folder not accessible by blinded study center staff. Specific instructions for use of the IWRS will be provided separately.

Randomization numbers will NOT be reused for any reason.

10.5 Analysis Cohorts

The All-Enrolled-Cohort (AEC) will include all screened participants who provide informed consent and screening or baseline assessments, regardless of the subject's randomization and treatment status in the study.

The Intent-To-Treat (ITT) cohort includes all participants in the AEC who were randomized.

The Safety-Cohort (SC) will include the participants in the AEC who receive a study vaccination. Participants will be analyzed as vaccinated, i.e., a subject will be assigned according to the vaccination received.

The Immunogenicity Cohort (IMC) will include all participants from the AEC who received the prescribed study vaccine or placebo and underwent at least one immunogenicity assessment after vaccination.

The Per-Protocol-Cohort (PPC) for will include all participants who meet all eligibility criteria, for whom the administration route and site of vaccine was according to protocol, have evaluable serum immunogenicity samples at baseline and at the time points of interest, were SARS-CoV-2 negative at baseline and had no major protocol deviations (PD) leading to exclusion. A major PD leading to exclusion from the PPC is defined as a PD that is considered to have a significant impact on the immunogenicity results. These will be identified prior to unblinding and analysis and may include:

- participants enrolled who did not meet study entry criteria
- participants who did not receive the correct study vaccine
- participants who developed withdrawal criteria but were not withdrawn
- participants who received a prohibited concomitant medication

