7.15 Prohibited During the Study

Receipt of the following vaccines and medications during the time periods listed below may exclude a participant from the per-protocol analysis from that point onwards, and may require vaccinations to be discontinued in that participant; however, it is anticipated that the participant would not be withdrawn from the study. Medications should not be withheld if required for a participant's medical care.

- Unless considered medically necessary, no vaccines other than study intervention should be administered within 28 days before and 28 days after each study vaccination. One exception to this is that seasonal and pandemic influenza vaccine can be given at least 14 days after, or at least 14 days prior to, the administration of study intervention.
- Receipt of chronic systemic treatment with known immunosuppressant medications, or radiotherapy, within 60 days before enrollment through conclusion of the study.
- Receipt of systemic corticosteroids (≥ 20 mg/day of prednisone or equivalent) for ≥ 14 days is prohibited from 28 days prior to enrollment through conclusion of the study.
- Receipt of inhaled/nebulized corticosteroids from 28 days prior to enrollment through conclusion of the study.
- Receipt of blood/plasma products or immunoglobulins within 60 days before enrollment through conclusion of the study.

- Prophylactic use of antipyretics and other pain medication to prevent symptoms associated with study vaccination are not permitted. However, if a study participant is taking a medication for another condition, even if it may have antipyretic or pain-relieving properties, it should not be withheld prior to study vaccination.

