8.7.1 Unblinding

Blinding will be guaranteed by the preparation of the study vaccine by an unblinded pharmacist or other qualified study-site personnel with primary responsibility for study vaccine preparation.

Participants will be randomly assigned to groups based on a computer-generated randomization schedule prepared before the study by or under the supervision of the sponsor and using the IWRS.

The investigator will not be provided with randomization codes. The codes will be maintained within the IWRS, which has the functionality to allow the investigator to break the blind for an individual participant.

Data that may potentially unblind the study vaccine assignment (e.g., immunogenicity data, study vaccine accountability data, study vaccine allocation, biomarker, or other specific laboratory data) will be handled with special care to ensure that the integrity of the blind is maintained and the potential for bias is minimized. This can include making special provisions, such as segregating the data in question from view by the investigators, clinical team, or others as appropriate until the time of database lock and unblinding.

Each phase of the study will be unblinded after DSMB review of safety data collected through Day 56. Some key personnel of the sponsor, not involved in study operations, may be unblinded at the time of Study Steering Committee analysis. The investigator may in an emergency determine the identity of the intervention by contacting the IWRS. While the responsibility to break the intervention code in emergency situations resides solely with the investigator, it is recommended that the investigator contact the sponsor or its designee if possible, to discuss the particular situation, before breaking the blind.

Telephone contact with the sponsor or its designee will be available 24 hours per day, 7 days per week. In the event the blind is broken, the sponsor must be informed as soon as possible. The date, time, and reason for the unblinding must be documented in the IWRS and in the source document. The documentation received from the IWRS indicating the code break must be retained with the participant's source documents in a secure manner.

Participants who have had their intervention assignment unblinded should continue to return for scheduled evaluations. Participants should not be allowed to receive further study vaccinations and are only to be followed for safety evaluation visits.

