10.6.3 Planned Interim Report

A planned interim report will be based on immunological testing and summary safety assessment up to and including Day 56, following unblinding of the study.

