4.5 Per-Protocol-Cohort (PPC)

The PPC will include all participants in the FAS who:

- met all eligibility criteria
- received all study vaccinations according to the protocol
- have evaluable serum immunogenicity samples at baseline and at the time points of interest
- had no major protocol deviations (PD) leading to exclusion.

Immunogenicity data will be censored (excluded) from immunogenicity analyses at all timepoints following the first date of (1) administration of a non-study (licensed) COVID-19 vaccine OR (2) positive SARS-CoV-2 test OR (3) onset of COVID-19 illness

Immunogenicity data will be censored (excluded) from immunogenicity analyses at all-time points following the first date of (1) administration of a non-study (licensed) COVID-19 vaccine OR (2) positive SARS-CoV-2 test OR (3) onset of COVID-19 illness

All immunogenicity analyses will be based on FAS and PPC.

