7 CHANGES FROM THE PLANNED ANALYSIS IN STUDY PROTOCOL

There are no changes to the analyses planned in the protocol. These analyses are subset to allow DSMB adjudication of the safety of VBI-2902a and VBI-2905a.

There will be unblinding in both Phase 1a and 1b of the study after Day 56, with an interim analysis conducted based on the Safety and Immunogenicity data , with a cutoff date at Day 56 (inclusive).

Final Statistical Analysis Plan (SAPP)

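### Per-protocol exclusions must be identified before unblinding, but each phase is unblinded after Day 56 and discretionary exclusions can arise to Day 336, so the safeguard cannot be met for late deviations

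*Protocol*

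**What the plan says.** Protocol 10.5 defines a major deviation for the PPC as "a PD that is considered to have a significant impact on the immunogenicity results". On timing it says: "These will be identified prior to unblinding and analysis and may include" four examples, the last being "participants who received a prohibited concomitant medication".

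Protocol 8.7.1 sets the unblinding: "Each phase of the study will be unblinded after DSMB review of safety data collected through Day 56". SAP 7 agrees: "There will be unblinding in both Phase 1a and 1b of the study after Day 56". Protocol 10.6.3 adds an interim report "based on immunological testing and summary safety assessment up to and including Day 56, following unblinding of the study".

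Protocol 7.15 says that a prohibited vaccine or medication "may exclude a participant from the per-protocol analysis from that point onwards". Four of its six categories run to the conclusion of the study: immunosuppressants or radiotherapy, systemic corticosteroids, inhaled corticosteroids, and blood products or immunoglobulins. Section 7.17 adds that participants may be eliminated for immune-altering conditions or immunological diagnoses arising during the study. Section 6.1.16 puts the end of study at Day 336.

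SAP 4.5 requires that PPC members "had no major protocol deviations (PD) leading to exclusion". It gives no list of deviations and no timing condition. SAP 4.4, 4.5 and 6.4 do censor immunogenicity data after the first non-study COVID-19 vaccine, positive SARS-CoV-2 test or COVID-19 illness.

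**The concern.** Classifying deviations before unblinding keeps knowledge of the arm out of the decision about who counts as per-protocol. A treatment first given, or a condition first diagnosed, after unblinding cannot have been classified before it. For these events the plan keeps the discretion and loses the protection. The wording is permissive in 7.15 and 7.17, and 10.5 rests on a judgement of impact on immunogenicity.

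At stake are the late PPC titers. Protocol 4.10 and 10.1.2 single out Day 224 (Phase 1a) and Day 168 (Phase 1b) as secondary time points. The Version 5.0 amendment rationale gives the longer-term antibody response as one reason for enlarging the Phase 1b placebo group from 9 to 27. In groups of 20 to 27, one or two discretionary removals can move a geometric mean visibly.

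There is also an ambiguity about earlier visits. Section 7.15 removes data from the event onward, whereas Protocol 10.5 and SAP 4.5 define the PPC by participant. A late deviation could be read as also removing that participant's Day 56 data, after the Day 56 results by group are known.

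**Working it through.** **Visit count.** Protocol 4.1 states 9 visits per phase. Screening + Day 1 + 7 post-dose visits = 9, so the stated figure is reproduced. Counting post-dose immunogenicity days (Protocol 4.10) later than Day 56:

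| Phase | Post-dose days | After Day 56 | Share |
|---|---|---|---|
| 1a | 7, 28, 35, 56, 112, 224, 336 | 112, 224, 336 | 3/7 = 42.9% |
| 1b | 7, 14, 28, 56, 84, 168, 336 | 84, 168, 336 | 3/7 = 42.9% |

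This is a scheduled maximum, because unblinding is one event per phase and not each participant's own Day 56. A participant enrolled L days before the last enrollee reaches visit day D before the last enrollee's Day 56 if L > D − 56. For the first late visit that is L > 112 − 56 = 56 days in Phase 1a and L > 84 − 56 = 28 days in Phase 1b. DSMB review time lowers both thresholds further.

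**Which deviations are exposed.**

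- Can be settled blind: entry-criteria failures, wrong vaccine, route and site of administration, baseline SARS-CoV-2 status, and prohibited treatment received before unblinding. The general other-vaccine window closes 28 days after each dose, and the antipyretic rule concerns prophylaxis around vaccination.
- Already rule-based: non-study COVID-19 vaccine, positive test and COVID-19 illness.
- Left over: the four 7.15 categories that run to study end, the 7.14 products without an earlier cut-off, and 7.17 conditions, where any of these first arises after unblinding.

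**Conflicts between the lists.** Section 7.14 ends the inhaled-corticosteroid period at Day 56, while 7.15 runs it to study conclusion. For systemic corticosteroids, 7.14 uses more than 14 days and 7.15 uses 14 days or more. Until these passages are reconciled, someone must choose which applies.

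**Size, hypothetical.** Let one participant in a group of n lie d log10 units below the mean m of the other n − 1. The mean of all n is m − d/n, and removal restores m, so the GMT is multiplied by 10^(d/n). The documents give no value for d; 0.5 to 1.0 is an assumption.

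- n = 20: 10^(0.5/20) = 1.059 and 10^(1.0/20) = 1.122, a rise of about 6% to 12%.
- n = 27: 10^(0.5/27) = 1.044 and 10^(1.0/27) = 1.089, a rise of about 4% to 9%.

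Drop-out and censoring would shrink n and enlarge these figures somewhat. The documents give no expected frequency of late deviations.

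**The case against.** The strongest reply is that little is left to exclude and little depends on it. Participants are healthy adults aged 18 to 54, screened for chronic and immune disease, so late immunosuppressants, blood products or immune diagnoses should be uncommon. Exclusion needs an actual recorded event; nobody can remove a participant at will. Immunogenicity is secondary, and Protocol 10.3 calls it exploratory. Every immunogenicity analysis is also run on the FAS, which has no general major-deviation exclusion, so a drift in the PPC would show. The SAP's fold-rise model is specified at Day 56, and the continuation criteria in Protocol 4.4 rest on Days 28 and 56. All of this stands and limits the weight of the point. It does not make the 10.5 condition achievable for a post-unblinding event.

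Two stronger readings are tempting, and the documents do not support them. A reader might infer that every PPC exclusion at the three late visits is a judgement made with the arm known. Most listed deviations can be classified blind by Day 56, and the COVID-19-related removals follow a date rule. A reader might also infer that someone who knows the arm and has seen the relevant titers decides who is removed. No section says who classifies deviations. Protocol 8.7.1 provides for segregating unblinding data until database lock and unblinding, and the interim report covers titers only through Day 56. The supportable statement is that nothing in the plan prevents an unblinded decision on late deviations.

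**Conclusion.** The point holds in a narrow form, and its severity is minor. Protocol 10.5 sets a timing condition that Protocol 8.7.1 and SAP 7 make impossible for deviations first arising after unblinding. SAP 4.5 omits the condition and offers no substitute for those deviations, although SAP 7 declares no change from the protocol's planned analyses.

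If membership is read visit by visit, as 7.15 implies, the effect is confined to the late PPC analyses: at most three of seven scheduled post-dose visits per phase. The illustrative shift of about 6% to 12% in a GMT assumes one removal from a full group of 20 and a gap of 0.5 to 1.0 log10. It shows sensitivity and does not predict bias.

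**What to change.** Amend Protocol 10.5 and SAP 4.5 as follows.

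1. Finalise the blinded PPC deviation list for visits through Day 56 before that phase is unblinded. State that later deviations do not change Day 56 membership.
2. For later visits, extend the SAP's existing date-driven censoring to the 7.14 and 7.15 products and the 7.17 conditions. Program it from the eCRF and remove data from the event date onward. Reconcile the conflicting 7.14 and 7.15 windows first; until then the rule cannot be coded.
3. Allow no discretionary PPC exclusion after unblinding.

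The cost is protocol and SAP wording plus some programming. Protocol 7.13 and 7.17 already require concomitant products, vaccinations and intercurrent conditions to be recorded in the eCRF, so no new data, visits or participants are needed. The small downside is the loss of case-by-case flexibility after Day 56.
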